Metadata outlining experimental design, collection procedures, analysis methods and dissemination will also be stored. Metadata will be freely available through published articles, dissertation theses and web-based content.

C. Access to Data and Data Sharing Practices and Policies

All intellectual property and data generated through this project will be administered in accordance with University of Michigan procedures and NIH granting agency policies (http://grants.nih.gov/grants/policy/data_sharing). The PI does not anticipate any legal or ethical issues that may hinder or prevent the sharing of data.

Study Title: Modulating interaction of motor learning networks in rehabilitation of stroke

Research outcomes will be made available through publication and presentation sources, subject to publisher subscription or printing charges. Experimental tasks, designs or methodological advancements will be made available for research use through publication and/or web-based material maintained by the Brain Behavior Laboratory (Director: [name]). Dissemination of research related materials will occur throughout the duration of the research plan as the information is validated internally and peer-reviewed. All data, experimental tasks, designs and methodological advancements for educational use will be made available through web-based material maintained by the Brain Behavior Laboratory.

To facilitate full access to all data generated as part of the proposed research a number of steps will be undertaken to protect participant anonymity. Data management will necessarily adhere to Federal Human Subjects Intuitional Review Board standards and the University of Michigan IRB. **All data will be encoded using participant codes. No personal information or personal identifiers will be linked to any of the data. Personal information and identifiers will be stored in locked and secured facilities.** Electronic copies of such information will be encrypted and stored on off-site servers. Access to these servers is restricted to approved laboratory personal through their unique username and password. Further, all University of Michigan researchers in the area of biomedical and health sciences are certified for research through the Program for Education and Evaluation in Responsible Research and Scholarship (PEERRS). **This includes any undergraduate students, graduate students, post-doctoral researchers and research assistants, who participate in research in the Brain Behavior Laboratory.** Certification of completion of the PEERRS program is maintained in the laboratory to ensure all personal have completed the program.

A full-time research assistant employed by the Brain Behavior Laboratory is currently responsible for monitoring all data collection, entry, and access to data collected in the laboratory.

D. Policies for Re-Use, Re-distribution and Production of Derivatives

The data generated from the current proposal will be of significant interest and benefit to a number of researchers and clinicians. Data will be made available only after data has been internally validated, relevant research hypotheses have been tested and study outcomes presented or published. In accordance with this policy it is likely that data will be made available no earlier than Year 2 of the proposed plan. All efforts will be made to accelerate this timeline provided scientific integrity is not compromised.

E. Data Archiving and Preservation

All raw and processed data, metadata, software (collection and analysis) will be archived locally on secured servers that are backed up at the University level on a daily basis. In addition to the dissemination strategies outlined above the Brain Behavior Laboratory will work with the Office of Research and Sponsored Projects (ORSP) at the University of Michigan to facilitate data archiving and preservation. ORSP is developing a Data Resource Sharing Center to support university researchers with data sharing and management (<http://orsp.umich.edu/datasharing/>).

Data and Safety Monitoring Plan

1. Plan for transcranial magnetic stimulation (including theta burst stimulation) monitoring

1.1 Subject Recruitment: All patients recruited will undergo repetitive rigorous screening to exclude individuals with an increased risk of developing a seizure or any other adverse reaction. The transcranial magnetic stimulation screening form to be used in the current study has been approved by the University of Michigan Medical School Institutional Review Board (IRBMED).

A waiver of informed consent will be used to perform screening over the phone prior to participant scheduling. The PI has successfully received a waiver of informed consent for other studies involving theta burst stimulation in younger and older healthy adults as well as stroke patients.

Screening results will be reviewed by [name] (Psychiatry) for suitability to participate. [name] is a Co-I on this application and has extensive experience using repetitive transcranial magnetic stimulation as a clinical intervention. [name] (Consultant) will also be available to review screening forms if a second opinion is needed.

Participants will be re-screened for contraindications to transcranial magnetic stimulation prior to each session involving any transcranial magnetic stimulation activities to ensure no changes in status. Should any change be reported (i.e. a new medication) [name] will re-evaluate the patient's risks and suitability for continued participation.

1.2 Training of all individuals who administer theta burst stimulation: All research personnel involved in the application of transcranial magnetic stimulation, including theta burst stimulation, will be familiar with published safety guidelines from the "Safety of TMS Consensus Group"⁸². Specifically, all personnel will be familiar with the procedures for patient screening for risk factors prior to participation as outlined in the informed consent document, the stimulation parameters to be used in this study, and first responder management in the event of a seizure. To facilitate first responder management our previously approved IRBMED approved adverse event protocols require two personnel be present at all times during stimulation regardless of study population.

1.3 Medical oversight of theta burst stimulation study protocol: In conjunction with the recommendations from the Safety of TMS Consensus Group⁸² [name] is designated as the principal investigator for the proposed work. Co-Investigator [name] is designated as the medically responsible physician. [name] is a medically licensed physician in the School of Medicine at the University of Michigan. He has extensive experience in the use of transcranial magnetic stimulation as a clinical treatment for depression. As Co-Investigator he is intimately familiar with the study protocol and was involved in the protocol design. [name] (or his designate) will review participant screening to determine suitability for participation.

1.4 Transcranial magnetic stimulation monitoring (including theta burst stimulation): All stimulation will be applied with at least two personnel present in the testing room at all times. Consistent with recommended guidelines⁸² for studies applying theta burst stimulation over non-motor cortical areas electromyography of the first dorsal interosseous of both the paretic and non-paretic limbs will be monitored for spread of excitation from the stimulation site over dorsolateral prefrontal cortex. The first dorsal interosseous was chosen as this muscle has one of the lowest thresholds for production of motor evoked potentials. All participants will also be visually monitored throughout the application of continuous theta burst stimulation. Personnel will be trained to watch the participant for time-locked behavior time to stimuli. In addition to overt time-locked motor responses personnel will also be trained to identify the more subtle signs and symptoms of frontal lobe seizures.

1.5 Seizure protocol: The PI has an IRBMED approved seizure protocol in place that is universal for all transcranial magnetic stimulation studies. This protocol is posted in visible locations at various points in the room where transcranial magnetic stimulation will be delivered. The protocol entails

Study Title: Modulating interaction of motor learning networks in rehabilitation of stroke

immediate activation of the Emergency Medical System (calling 911). Average EMS response times from the Ann Arbor Fire Department are 4.3 min. The site at which the transcranial magnetic stimulation protocol will be performed is less than 1 mile from the Emergency Department at the main University of Michigan Hospital and 1.1 miles from the nearest Ann Arbor Fire Department station. In the event that a seizure is not self-limited, the arrival of an EMS team should coincide with the appropriate time to administer therapy for status epilepticus, including anticonvulsant medications, EKG monitoring, and advanced life support protocols.

1.6 Adverse events arising in the course of participation: A Serious Adverse Event (SAE) in this study will be defined as an event that results in death, is life-threatening, requires hospitalization or prolongation of existing hospitalization, or results in persistent or significant disability or incapacity. The degree of probable relation between study procedures and the SAE will be carefully evaluated and documented.

1.6.1 Serious adverse events will be reported to the IRBMED within 7 days of occurrence (or notification) of the event if they are definitely or possibly related to the study interventions. In the case of death occurring within 30 days of a study-related intervention, reporting to the IRBMED will occur within 7 days of the event (or notification of the event) regardless of relatedness to the study. For SAEs that are definitely not related to the study, reporting will occur at the time of scheduled continuation, per standard reporting timetable of the University of Michigan IRBMED.

1.6.2 Unexpected adverse events in this study will be defined as any adverse events for which the nature and severity are not consistent with expected or anticipated adverse events resulting from participation in the protocol.

1.6.3 Adverse events not determined as serious will be graded as moderate or mild. Moderate is defined as any non-serious event which causes discomfort and requires treatment, but does not pose any significant or permanent risk or harm to the subject or require in-patient hospitalization, including social or psychological trauma causing moderate or temporary distress, significant embarrassment, stigmatization of individual or community/ group, disruption of familial/social relationships or nontrivial emotional distress or upset. Moderate adverse events will include evaluation in the emergency room not leading to hospitalization. Mild is defined as any non-serious event of less than moderate severity.

1.6.4 Moderate adverse events that are expected will be reported to the IRBMED at scheduled continuation review. Moderate adverse events that are unexpected and definitely or possibly related will be reported to the IRBMED within 14 days of occurrence. Moderate adverse events that are unexpected and definitely not related will be reported to the IRBMED at scheduled continuation review.

1.6.5 Expected, mild adverse events will not be reported to the IRBMED. Unexpected, mild AEs will be reported to the IRBMED at the scheduled continuation review.

1.7 Reporting responsibility: [name] (Primary Investigator) will have ultimate responsibility for event reporting. [name] will consult with [name] to determine the classification of the adverse event and draft the adverse event report. The study team will conduct regular meetings to discuss review the prevalence of expected mild adverse events. Moderate or severe adverse events, expected or not will trigger an immediate review of study procedures and adverse event response outside of these monthly meetings.

2. *Incidental findings arising from assessment*

Study Title: Modulating interaction of motor learning networks in rehabilitation of stroke

The current protocol involves magnetic resonance imaging research scans. Incidental findings discovered in the course of a research scan have the potential to raise significant anxiety in subjects, while the nature of a research scan seriously limits the usefulness of the scan for resolving an incidental finding. At the first level, it is critical to make all participants aware of this risk. Another important consideration is to make subjects aware that they are receiving a research scan, which cannot be used to assess the clinical significance of any finding.

Standard operating procedure at the University of Michigan fMRI center does not entail reading of research MRI scans by neuroradiologists. Nevertheless, the experienced technicians and investigators collecting research data do encounter anomalous incidental findings, such as the presence of a large cyst or tumor. A protocol is in place to handle these events.

2.1: Discovery of a finding: Incidental findings that arise in the course of assessment, such as an abnormal finding in the MRI, will be brought to the immediate attention of the PI.

2.2 Gathering additional information: The PI will review the finding and seek consultation with [name] and others as appropriate.

2.3 Informing the subject: If the [name] is available while the subject is being scanned, and can assess the finding and make a determination about informing the subject that will be done immediately. If [name] is not available for a face-to-face meeting with the subject, study staff are instructed to complete as much of the protocol as is reasonable, without revealing the existence of an anomaly. The intention here is to control the circumstances by which the subject is informed of the anomaly, making sure that [name] (a board certified psychiatrist) is the person who talks to the subject, can answer questions and gauge the emotional reaction of the subject to the news. The subject will be informed by [name] personally, either through a phone call or a face-to-face meeting. While a face-to-face meeting is preferred, this may not be immediately convenient for the subject, [name] and [name] will weigh the relative benefits of the more personal setting versus anxiety engendered by anticipating a meeting to discuss something the subject did not expect to hear.

2.4 Informing the subject's health care provider: Arrangements will be made to provide a summary of the finding to the subject's personal physician, with the patient's permission. The information conveyed will recommend that a follow-up, clinical MRI be obtained to evaluate the incidental finding.

2.5 Informing the local IRB: The incidental finding will be reported to the IRB as an adverse event, with a gradation appropriate to the severity of the finding.

3. Procedures for dealing with suicidal thoughts, plans and intentions

Study personnel will be alert for the emergence of new suicidal thoughts amongst enrolled subjects during the course of participation. The PI will be promptly notified of any suspect comments or behaviors and consult with [name] (a board certified psychiatrist). [name] and [name] will formulate subsequent plans for additional emergency evaluation at the psychiatric emergency room (University of Michigan Psychiatric Emergency Services), if appropriate. Similarly, if the evaluation of a potential subject uncovers suicidal plans or intentions, the same procedures for emergency evaluation will be followed.

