Modulating interaction of motor learning networks in rehabilitation of stroke

NCT03086551

January 10th, 2018

SPECIFIC AIMS

Aim 1: Determine whether cTBS over contralesional dorsolateral prefrontal cortex prior to motor practice enhances motor learning post-stroke. Aim 1 will compare the efficacy of contralesional cTBS over dorsolateral prefrontal cortex paired with motor practice versus sham cTBS paired with practice for improving motor function.

Aim 2: Determine the effects of cTBS over dorsolateral prefrontal cortex upon motor networks. Our second aim is to determine the effect of our cTBS intervention upon local intracortical networks within primary motor cortex and across the motor network.

Aim 3: Provide preliminary evidence for individual predictors of the efficacy of dorsolateral prefrontal cortex cTBS post-stroke. Within our exploratory third aim, we will examine the relationship between pre-intervention behavioral and brain metrics and the responsiveness to dorsolateral prefrontal cortex cTBS.

RESEARCH STRATEGY

Design

Aims 1, 2 and 3 will be assessed in a single experiment. 16 individuals with first time middle cerebral artery (MCA) territory ischemic stroke will serve as their own matched control in a cross-over design. Each arm of the cross-over design will include the same 6 sessions (Figure 1). Each session within an arm of the cross-over design will be separated by at least 24 hours and the duration of each arm will not exceed three weeks. The only difference between the arms of the study will be the delivery active cTBS or sham cTBS over dorsolateral prefrontal cortex. The order of each arm will be counterbalanced. The four-session duration of the proposed intervention was informed by our past work pairing sensorimotor cortical stimulation with the same serial targeting task to be employed here. A three-week break between study arms will be employed to minimize carry over effects between each arm of the study. Therefore, total duration of the study from enrollment to completion

[figure not shown]

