Figure 1 – Experimental procedure for one arm of the cross-over design. Both arms of the design will be similar. The only difference will be the NIBS intervention). A three-week break will separate Session 6 from Arm 1 to Session 1 of Arm 2. Sessions 1 and 6 are expected to take ~2.5 hours to complete. Sessions 2 thru 5 are expected to take ~1.25 hours to complete. SR task – serial reaching task. PANAS - Positive and Negative Affect Schedule

will be approximately 9 weeks (~3 weeks to complete arm 1, a 3 week break, ~3 weeks to complete arm 2).

Inclusion Criteria: 1) Age between 40-75 years, 2) movement-related deficit associated with first time middle cerebral artery stroke, 3) greater than 3-months post-stroke, 4) Fugl-Meyer score between 15 and 66 and 5) ability to elicit a motor evoked potential from the ipsilesional cortex.

Exclusion Criteria: 1) a score <23 on the Mini-Mental Status Exam, 2) a history of seizure/epilepsy, head trauma, major psychiatric diagnosis, neurodegenerative disorder or substance abuse, 3) a history of congestive heart failure, 4) systolic blood pressure above 120 mmHg and/or diastolic pressure above 80 mmHg, 5) the taking of any GABAergic, NMDA-receptor antagonist or other drug known to influence the neural receptors that facilitate neural plasticity, 6) an infarct resulting from ischemic stroke of anterior or posterior cerebral artery OR an infarct that encroaches within 2cm of the site of cTBS stimulation, 7) absence of an MEP in response to single pulse transcranial magnetic stimulation over ipsilesional M1 and 8) any other contraindication to TMS.

Behavioral Test Battery: Serial reaching task: Motor performance will be indexed with a serial reaching task (Aim 1) (Figure 2). This task was chosen as: 1) it involves a reaching motion similar to that emphasized during rehabilitation, 2) we can quantify the effects of dorsolateral prefrontal cortex stimulation upon procedural knowledge tied to larger movement sequences in addition to sensorimotor control of simple reaching and 3) we can assess declarative knowledge about the practiced task. We developed and have previously published with this task confirming it can be performed and learned by our prospective stroke patient participants.

Patients will perform reaches with their paretic arm between sequentially presented targets using a touch screen. Each target will appear once patients have come to a complete stop within the target for 500ms.

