Prior to each arm of the cross-over design patients will be informed of a repeated sequence of six targets that they will be required to reach to. Different sequences matched for difficulty will be used in each arm. Free recall will be performed prior to each session to assess any change in declarative knowledge.

During Sessions 2, 3, 4 and 5 of each cross-over arm participants will complete 30 reaches where the targets will occur in a random series. Participants will then complete a block of 60 reaches where the 6-element sequence will repeat 10 times. An additional block of 30 random reaches will then be completed. The pre-stimulation reaches will be used to assess sustained change in performance from session to session. This same set of 120 reaches will also be performed during Session 6 as a retention test.

For Sessions 2, 3, 4 & 5 participants will receive either active or sham cTBS over dorsolateral prefrontal cortex following the initial set of 120 reaches. Post-stimulation

[figure not shown]

Figure 2 – Serial Targeting task. Participants will be seated in front of a touch screen angled on a desk in front of them and be asked to touch sequentially presented targets using their paretic limb. Targets will be presented sequentially at one of nine locations (inset bottom left).

Study Title: Modulating interaction of motor learning networks in rehabilitation of stroke

participants will complete an additional 270 targeted reaches comprised solely of the 6-element repeating sequence.

The primary dependent measure for Aim 1 will be total response time to complete the sequence. As patients must stop within the target this metric captures both speed and accuracy. Comparison of response times during random reaches across session will be used to index sensorimotor procedural knowledge. Comparison of the difference between repeated and random reach response times will be used to index development of procedural knowledge relating to a larger sequence of movements.

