The statistical approach and power analyses were developed in consultation with the Center for Statistical Consulting and Research at the University of Michigan. For Specific Aim 1 (**Determine whether cTBS over contralesional dorsolateral prefrontal cortex prior to motor practice enhances motor learning post-stroke**) the primary outcome metric will be response time during random reaches. The extent of sensorimotor procedural knowledge will be assessed using an Arm (active-cTBS, sham-cTBS) x Session (Session 2, Session 6) repeated measures ANOVA. The extent of procedural knowledge relating to the larger movement sequence will be assessed using a Arm (active-cTBS, sham-cTBS) x Sequence (Random, Repeated) x Session (Session 2, Session 6) repeated measures ANOVA. As a secondary assessment, the rate of procedural learning will be assessed for each measure by including Sessions 3, 4 and 5 as levels of the factor Session. An Arm (active-cTBS, sham-cTBS) x Session (Session 1, Session 6) repeated measures ANOVA will be used to assess time to complete the Jebsen-Hand Function Test

For Specific Aim 2 (**Determine the effects of cTBS over dorsolateral prefrontal cortex upon motor networks**) two separate sets of analyses will be performed. First, separate Arm (active-cTBS, sham-cTBS) x Hemisphere x Time (Session 1, Session 6) repeated measures ANOVA will be performed to assess change in intracortical motor networks (recruitment curves, short-latency afferent inhibition) across study arm. Motor evoked potential amplitude will be the dependent variable. Arm x Hemisphere x Time interactions will be decomposed using separate Arm x Time repeated measures ANOVAs for each Hemisphere.

Second, to assess changes in intercortical neural networks group level maps for each identified component in the independent component analysis will be assessed using separate Arm x Sequence random-effects analysis for Session 1 and Session 6. Statistical threshold will be set to $p < 0.05$ and corrected for multiple comparisons using the false discovery rate.

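### The plan does not say how the practised sequences are assigned to active and sham cTBS, or that order is randomised, and it models neither sequence version nor period

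*Combined protocol and SAP*

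**What the plan says.** **Assignment.** The Design section describes a two-arm cross-over in 16 participants and says "The only difference between the arms of the study will be the delivery active cTBS or sham cTBS over dorsolateral prefrontal cortex". On order it says only "The order of each arm will be counterbalanced". The serial reaching task section adds a second difference between arms, the practised six-target sequence: "Different sequences matched for difficulty will be used in each arm". No section gives the rule that links a sequence to a stimulation condition, the number of versions, or the evidence for the matching.

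**The word arm.** In the Design sentence on stimulation and in the analysis section, arm is the condition, active or sham. In the Figure 1 legend it is the period: "A three-week break will separate Session 6 from Arm 1 to Session 1 of Arm 2".

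**Analysis.** Under Statistical Analyses and Power, Aim 1, "the primary outcome metric will be response time during random reaches", tested with an "Arm (active-cTBS, sham-cTBS) x Session (Session 2, Session 6) repeated measures ANOVA". Sequence learning is tested with an "Arm (active-cTBS, sham-cTBS) x Sequence (Random, Repeated) x Session (Session 2, Session 6) repeated measures ANOVA". The factor Sequence there means random versus repeated reaches, not version A versus version B. Neither model has a term for version, order or period. The serial reaching task section names a different primary measure, the total response time to complete the sequence.

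**The concern.** In a cross-over study of learning, each participant needs fresh material in the second period, so using two sequences is sensible. The material must then be assigned so that it does not travel with the treatment. Balancing the order of active and sham does not ensure this. If version A is always practised under active cTBS and version B always under sham, every participant carries the same version difference in the active-minus-sham comparison, whichever came first. An easier-to-learn version would look like a cTBS effect, and no later analysis could separate the two.

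At stake are the Arm x Sequence x Session test, which is the plan's test of sequence learning, and sequence completion time. Because the plan does not say that order is assigned at random, chance assignment cannot be relied on to break any link between version and condition.

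**Working it through.** **1. What each reading of arm implies**

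Let D be one participant's active-minus-sham contrast in change from Session 2 to Session 6:

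D = τ + πO + δV + error

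Here τ is the cTBS effect, O = ±1 for order, and V = ±1 for which version was practised under active cTBS.

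| Assignment of version | V across participants | Consequence for τ |
|---|---|---|
| Tied to condition | same for everyone | estimate is τ ± δ; not separable |
| Tied to period, order 8/8 | equals ±O | no bias; version is aliased with period |
| 2 orders x 2 versions, 4 each | orthogonal to O | no bias; version and period both estimable |

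A version that is harder by a constant amount at both sessions cancels in the change from Session 2 to Session 6. Only a difference in learning between versions contributes to δ. Random reaches do not use the practised sequence, so δ enters the three-way contrast only through its repeated-sequence half.

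**2. The plan's own figure**

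The plan gives no figure for this point. Its sample-size range is 5 to 12 for power 0.80, alpha 0.05 and correlation 0.7. A repeated-measures F test with f² = η²/(1−η²), λ = f²·N·m/(1−ρ), m = 4 cells and 1 numerator df (m and df are my assumptions) gives N = 12 for η² = 0.06, 8 for 0.107, 6 for 0.135 and 6 for 0.16. That is close to the stated range. It does not decide this point, but it supports carrying the correlation of 0.7 forward.

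**3. Version tied to condition: size for the planned three-way test**

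Inputs: n = 16 and ρ = 0.7 (Statistical Analyses and Power); alpha 0.05, two-sided; no true cTBS effect. Learning differences of 0.1, 0.25 and 0.5 SD of a single response-time measurement are assumed, because the documents give none.

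The contrast adds eight cell means with weights ±1, so with equal correlations its variance is 8(1−ρ) = 8 x 0.3 = 2.4 and its SD is 1.549. The non-centrality is δ√16/1.549, on 15 df.

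| Assumed difference | Non-centrality | False-positive rate |
|---|---|---|
| 0.1 SD | 0.258 | 5.7% |
| 0.25 SD | 0.645 | 9.3% |
| 0.5 SD | 1.291 | 22.7% |

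**4. Version tied to period: what remains**

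Scale D to SD 1. Suppose that version and period together shift D by ±0.5 SD according to order (assumed). With 8 participants per order and no order term, the expected sample variance of D rises from 1 to 1 + 0.25 x 16/15 = 1.267. In simulation the type I error falls to about 3%. Power for an effect of 0.75 SD falls from 0.80 to 0.72. With order in the model, power is 0.797.

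The section on potential problems expects some participants to be lost between arms. If completers split 8 and 4 by order, the estimate without an order term is biased by (8 x 0.5 − 4 x 0.5)/12 = 0.17 SD.

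**5. Four cells of four, with order and version in the model**

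Bias from a version main effect is 0 and type I error is 0.050. Residual df fall from 15 to 13, and power at 0.75 SD goes from 0.801 to 0.792. With 2 or 4 random losses, the variance of the adjusted effect rises on average by about 2% or 5% (worst case with 4 losses: 50%), on top of the smaller n.

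**The case against.** The best defence is that the plan describes sound practice briefly. The sentence before the one on different sequences is about time: participants learn their sequence before each arm begins. The Figure 1 legend also treats arms as first and second periods. Read that way, with order balanced, version is aliased with period and not with cTBS, and there is no bias. This stands, and it limits the conclusion.

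A reader might infer that the plan confounds sequence with active cTBS. The documents do not support that. They are silent on the assignment, and one of the two available readings is free of bias.

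A reader might also infer a larger error rate by testing Arm x Session on sequence completion time. There the contrast SD is √(4 x 0.3) = 1.095, and differences of 0.25 and 0.5 SD give 14% and 40%. The arithmetic is right, but the analysis section lists no such ANOVA; its two-way test is on random reaches.

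Three further points stand. The sequences are said to be matched for difficulty, so a small residual difference is plausible, and at 0.1 SD the effect on error is slight. The random-reach outcome that the analysis section calls primary is not directly exposed, nor are the Jebsen, TMS and imaging measures, which do not have the practised sequence as their outcome. Predictable order in a within-person comparison does not itself create the version confound, and I have not put a size on it.

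The ambiguity itself is not a defence. The same text permits an assignment from which the sequence-learning result could not be attributed to stimulation.

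**Conclusion.** The concern holds as a gap in specification with a concrete consequence. The plan should state how versions are assigned and how order is assigned, and should model version and period.

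If version follows condition, the sequence-learning test and sequence completion time are fully confounded with any version difference in learning. If version follows period, the estimate is unbiased while order stays balanced, but the planned ANOVA has an inflated error term and is open to bias from uneven dropout.

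The rates of about 6%, 9% and 23% are illustrations. They apply only if version is tied to condition, and they rest on assumed differences, a common correlation of 0.7 and equal variances. How exposed the trial's primary result is depends on which of the two stated primary measures is meant, and the documents should reconcile these.

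**What to change.** - Keep the commitment to match the sequences for difficulty, and state how the matching was done.
- Add an allocation rule. For two versions: participants are allocated by a computer-generated list, concealed until the first session of the first period, in randomised blocks of four, to one of four cells (active first or sham first, crossed with version A or version B under active cTBS). At n=16 this gives 4 per cell.
- Include period (through order) and sequence version as terms in the sequence analyses, and in the mixed model that the plan holds in reserve for dropout.
- Use one word for condition and another for period throughout. Amend the statement that stimulation is the only difference between arms.

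The change needs an allocation list and two model terms, with no added participants or visits. It uses 2 residual degrees of freedom, about one point of power. Balance will be only approximate after dropout. Crossing removes the main effect of version but not an interaction in which cTBS works differently on the two sequences.
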